- Diagnosis of individuals in the AD biological continuum with evidence of amyloid-beta accumulation based on the presence of A β load AD biomarkers (either in CSF or PET scan), MMSE, CDR score and cognitive tests as defined by the Guidance document of EMA (2016) or FDA (2018):
 - preclinical AD: MMSE \geq 27 and CDR=0, either none or borderline cognitive deficits (compatible with FDA stages 1 and 2, with positive AD biomarkers). Patients reporting subjective cognitive decline who meet the criteria above are eligible for assignment to the preclinical AD group.
 - prodromal AD/MCI due to AD: MMSE >23, CDR=0.5, impairment on cognitive testing with RBANS (compatible with stage 3 FDA, with positive AD biomarkers).
 - mild to moderate AD dementia: (MMSE>17, CDR>0.5, compatible to FDA stages 4-5).
- Informed consent signed by the subject and informant.
- In otherwise-good health condition, or with diagnosis mild chronic disorder (of metabolic, respiratory, immunological, cardiologic, and metabolic origin) or any other affections that are controlled by therapy and/or do not impair function on a secondary basis to that of AD-related symptomatology.
- Subject and caregiver should be able to read and communicate in the language of the recruitment centre and available to actively engage in tests and questionnaires.
- Subject and the caregiver/family member or informant own a smartphone.
- For those volunteering in the sub-study, their house should allow appropriate Wi-Fi and/or phone line connectivity.
- For those volunteering in the sub-study, signature on an additional Informed Consent (specifically regarding the activation – deactivation of the device during activities considered private and personal).

Healthy Control subjects (n=215):

- Male or female over 50 years of age.

Evaluation of a Computerized Complex Instrumental Activities of Daily Living Marker (NMI) (AltoidaML)

- Individuals in the AD biological continuum with no evidence of amyloid-beta accumulation based on the presence of A β load AD biomarkers (either in CSF or PET scan).
- Approximately age and gender matched to AD subjects on a group level.
- A caregiver/family member or informant is available to collaborate.
- MMSE >27, CDR=0, no cognitive deficits at the screening visit.
- In otherwise good health conditions, or with diagnosis mild chronic disorders (of metabolic, respiratory, immunological, cardiologic, and metabolic origin) or any other affections that are controlled by the therapy and do not importantly limit ADLs or social interactions.
- Able to read and to communicate in the language of the recruitment centre.
- Informed consent signed by the subject and caregiver.
- Subject and caregiver own a smartphone.
- For those volunteering in the sub-study, their house should allow appropriate connectivity.
- For those volunteering in the sub-study, signature on an additional Informed Consent (specifically regarding the activation – deactivation of the device during activities considered private and personal).

5. Exclusion criteria

A potential subject who meets any of the following criteria will be excluded from participation in this study:

For Alzheimer's disease subjects:

- Presence of an additional neurological or psychiatric disease that may affect ADL, cognitive function or social interactions.
- Abnormal VB12 value.
- Any other kind of disorders that relevantly affect mobility and/or ADL, cognitive function or social interactions (e.g., immune-mediated inflammatory disorders, recovery from recent trauma, stroke confirmed by MRI, etc.).
- TSH above normal range
- T3 or T4 outside normal range with clinically significant.

Healthy Control subjects:

- Presence of an additional neurological or psychiatric disease that may affect ADL, cognitive function or social interactions.
- Diagnosis of any disorders or post traumatic conditions that are not fully controlled by the therapy and produce relevant limitations of ADL, cognitive function or social interactions.

[figure not shown]
Evaluation of a Computerized Complex Instrumental Activities of Daily Living Marker (NMI) (AltoidaML)

6. Sample size calculation

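### Controls and preclinical AD are drawn from one cognitively normal pool but admitted under different MMSE, deficit and laboratory rules, which can add a difference not due to amyloid

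*Combined protocol and SAP*

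**What the plan says.** Section 3, under Population, describes controls and preclinical AD together as cognitively normal and asks each site for equal numbers of amyloid-positive and amyloid-negative people among them. The lists under Inclusion criteria and Exclusion criteria then set these rules:

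| Rule | Preclinical AD | Healthy controls |
|---|---|---|
| MMSE and CDR | "MMSE \geq 27 and CDR=0" | MMSE above 27, CDR 0 |
| Cognitive deficits | "either none or borderline cognitive deficits" | none at screening |
| B12 | excluded: "Abnormal VB12 value" | no rule listed |
| Thyroid | excluded: "TSH above normal range", plus a T3/T4 rule | no rule listed |

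The control wording in full is "MMSE >27, CDR=0, no cognitive deficits at the screening visit".

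The Introduction defines FDA stage 2 as AD pathology with detectable abnormality on sensitive neuropsychological tests but no functional impairment. The preclinical group is meant to span stages 1 and 2. The Introduction also names separating these stages from healthy controls among the most important results sought. In Sample size calculation, controls versus preclinical AD is the first of three powered comparisons.

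Matching is on age and gender at group level. The Statistical Analysis section names age and sex as covariates, with other covariates left open.

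**The concern.** If two groups are to be compared by amyloid status, a rule applied to only one of them shifts that group for reasons other than amyloid. Here the lower end of normal cognition is removed from the controls only. An amyloid-negative person with CDR 0 and MMSE 27, or with a borderline deficit, has no group to enter. The same person with a positive amyloid test is enrolled as preclinical AD.

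The Altoida assessments target orientation, planning, memory and executive function, so they are likely to track what these rules select on. Part of an observed difference could then appear even if amyloid had no effect. Age and sex matching and adjustment do not remove it. The multivariate step, which predicts study group, could also partly learn the eligibility rule. At stake is how the early-detection result is read.

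**Working it through.** **What the plan fixes.** The stated size is 55 per group, for 80% power that all three Holm-adjusted two-sided Welch tests succeed. The means and interquartile ranges behind it come from a figure in a cited study and are not in the documents, so 55 cannot be reproduced. As a yardstick only, I simulated four groups of 55 with equal steps and a common SD (both assumed). Power for all three tests is 0.78 at a step of 0.66 SD and 0.83 at 0.68 SD, so 55 per group corresponds to about 0.67 SD per step.

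**MMSE rule alone.** All inputs are assumed: the distribution of scores 27 to 30 among eligible people, the correlation r between the digital outcome and MMSE, and no amyloid effect. Controls lose everyone at 27.

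- Gap = mean without score 27 − mean with it.
- Spurious difference d = r × gap / SD.

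| Shares at 27/28/29/30 | Mean with 27 | Mean without 27 | Gap | SD | Gap in SD |
|---|---|---|---|---|---|
| 5/15/30/50% | 29.25 | 29.37 | 0.12 | 0.89 | 0.13 |
| 10/20/32/38% | 28.98 | 29.20 | 0.22 | 0.99 | 0.22 |
| 17/23/30/30% | 28.73 | 29.08 | 0.35 | 1.07 | 0.33 |
| 25/25/27/23% | 28.48 | 28.97 | 0.49 | 1.10 | 0.45 |

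With r from 0.2 to 0.5, d runs from 0.2 × 0.13 = 0.03 to 0.5 × 0.45 = 0.22.

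With 55 per group the standard error is √(2/55) = 0.191. The chance of an unadjusted two-sided p < 0.05 is Φ(d/0.191 − 1.96) + Φ(−d/0.191 − 1.96). This is about 5% at the low end and 22% at the high end.

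**Deficit rule.** The protocol does not say what share of otherwise eligible people has a borderline deficit. Assume that normally distributed cognition loses its lowest share b among controls only. The shift is φ(z_b)/(1 − b), where z_b is the normal quantile at b.

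- b = 5%: 0.103/0.95 = 0.11 SD. With r = 0.3, d = 0.03 and the chance of p < 0.05 is 5.3%.
- b = 30%: 0.348/0.70 = 0.50 SD. With r = 0.7, d = 0.35 and the chance is 45%.

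The two rules overlap, because people at MMSE 27 are more likely to have a borderline deficit. The two ranges should not be added.

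**Laboratory rules.** Removing abnormal B12 and thyroid values from AD subjects only would tend to make that group healthier than the controls and so narrow the gap. The documents give no prevalence or effect from which to size this.

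**With aligned rules.** If both groups meet the same cognitive and medical rules, the difference caused by those rules is zero by construction. The stated sample size does not depend on them.

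**The case against.** The best counter-argument is that the cognitive gap belongs to the disease definition. Preclinical AD is described as "either none or borderline cognitive deficits (compatible with FDA stages 1 and 2, with positive AD biomarkers", and stage 2 has detectable abnormality by definition. This stands in part. A reader might infer that the two groups should differ only by amyloid and that any cognitive gap is artefact. The documents do not support that, because the contrast sought is stages 1 and 2 against controls. What remains is the one-sided bar on amyloid-negative people at the same cognitive level.

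Second, the MMSE difference may be loose notation. Dementia subjects need MMSE above 17 under Inclusion criteria, yet the ethics section on incapacitated subjects gives 17 as the minimum. If above 27 was meant as 27 or more, the MMSE component vanishes. This cannot be settled from the text. The deficit rule would remain.

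Third, a reader might infer that stroke is left open for controls, since MRI-confirmed stroke is named only on the AD side. That does not follow. It appears there as an example under "Any other kind of disorders that relevantly affect mobility and/or ADL, cognitive function or social interactions", and controls are excluded for neurological disease that may affect the same functions.

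Fourth, the effect may be small and its net direction is unknown. This stands. It is also why the two sets of rules cannot be assumed to cancel.

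**Conclusion.** The eligibility rules differ between the two cognitively normal groups on MMSE, cognitive deficit, B12 and thyroid function, and nothing the plan names balances them. This can add a difference to the first powered comparison that is not due to amyloid. Under the assumptions above, the MMSE rule alone gives about 0.03 to 0.22 SD, or 4% to 33% of the 0.67 SD step implied by 55 per group. The deficit rule, taken separately, gives 0.03 to 0.35 SD, at most about half that step. The laboratory exclusions may offset some of this.

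A reader might infer that the bias is known to inflate the contrast. The documents do not support a net sign or size. Every score distribution, deficit share and correlation used here is assumed. The point is worth acting on because the remedy is cheap and the comparison is central.

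**What to change.** 1. State one MMSE limit for both cognitively normal groups, and reconcile the use of greater-than and at-least signs throughout the eligibility text.
2. Reconcile the B12 and thyroid exclusion lists between the groups, or state why they differ.
3. Pre-specify a sensitivity analysis of controls versus preclinical AD limited, in both groups, to MMSE 28 or more and no cognitive deficit. This is in effect stage 1 against controls. Report it beside the stage 1 and 2 comparison. The protocol gives no test or cut-off separating no deficit from a borderline one in these groups, so define that first.
4. Use adjustment for baseline MMSE at most as a further sensitivity analysis. It cannot restore the amyloid-negative people who were never enrolled, and it may remove a real stage 2 effect.

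The cost is mainly amendment wording and one additional analysis, with no change to the sample size. There are two downsides. The restricted analysis has fewer preclinical subjects and answers a narrower question. Aligning the laboratory exclusions may also need B12 and thyroid results for controls: the baseline blood list in section 4.4.2 does not include them, and under section 4.4.1 eligibility is judged from existing records and an interview, before baseline sampling.

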4. METHODS

Evaluation of a Computerized Complex Instrumental Activities of Daily Living Marker (NMI) (AltoidaML)

7. Study procedures

For the Schedule of Activities listed in tables 1 and 2, a CRF schedule of activities will be prepared and shared with the recruitment sites. A Global Unique Identifier (or equivalent) will be generated and associated with each subject and used for all datasets regarding that subject, e.g., all clinical information, RMT generated data, anonymization procedures.

Clinical information will be collected in the following occasions:

- Main study
 - screening, either by phone or as a visit;
 - baseline visit at the clinic;
 - study-end visit at the clinic;

Up to three phone calls will be performed during the main study and the sub-study, respectively, to monitor the adherence, collect Adverse Events and provide technical support.

4.4.1. Screening

Subjects will be recruited from the Memory Clinics either from an available database (via phone interview), new individuals attending the clinics with interest in the study and the appropriate entry criteria, or following the referral of colleagues, medical institutions or patient advocacy groups. Information critical to assess a subject's eligibility will be collected from the available clinical notes, exams and tests results, the subject medical history and from an interview (by phone or in person) with the subject. In particular, evidence of the following will be sought: (a) diagnosis, (b) positive beta-amyloid biomarkers determined either via CSF or amyloid-PET imaging, (c) Mini-Mental State Examination (MMSE) score and Clinical Dementia Rating (CDR) score obtained 6 months or less before the time of the screening interview, (d) relevant comorbidities that reduce the daily functioning capacities of the subjects, and other information coming from the notes of relevance as entry or exclusion criteria confirmed by MRI. During the interview, other information will be exchanged. For example, a brief motivational introduction for the relevance of this study will be followed by question aimed to understand the interest of the subject to enter into the study, her/his ability to use a smartphone, the agreeability wearing digital devices and having a caregiver/family member/informant interested to support them for the period of the study. If most of the entry criteria are fulfilled, a copy of the Informed Consent Form (ICF) will be sent and/or given to the subjects and to caregiver/family member/informant some days before the baseline visits and discussed again during the interview. Subjects and caregivers will receive a separate ICF for their respective signature. A specific addendum to the IC will be provided regarding the sub-study with at home monitoring.

Evaluation of a Computerized Complex Instrumental Activities of Daily Living Marker (NMI) (AltoidaML)

4.4.2. Main study, baseline visit

Both the study subjects and informant will be requested to be present at the baseline visit. At the baseline visit, a recap of the eligibility of the subject for the study will be made. Prior to the first data collection procedures, the ICF will be signed by the study subject, caregiver/informant, and the physician/researcher representing the clinical site. Both the study subject and the caregiver/informant will receive a copy of the signed document.

The following clinical information will be collected either via interview or based on recent (less than 6 months) medical notes or documentation (see table 1 and section 5.1 for a more elaborate description):

- Demographics.
- Medical history.
- Medication use.
- Physical examination (including BMI, vital signs).
- Diet supplement use.
- Godin Leisure-time exercise questionnaire.
- Edinburgh Handedness Inventory Form.
- Smoking habit.
- Drinking habits.
- Blood samples and CSF will be collected for (a) metabolic markers, plasma cholesterol and HbA1S level, (b) genetic analysis and (c) biobanking.

Rating scales rated by physician (or rater) by interviewing the subjects:

- CERAD neuropsychological test batter, including MMSE (as longitudinal assessment)
- Geriatric Depression Scale – short form (GDS)

Rating scale rated by Physician (or rater) by interviewing the caregiver/informant:

- CDR (as longitudinal assessment)
- Amsterdam IADL.
- Alzheimer's Disease Cooperative Study (ADCS) scale:
 - ADL in mild and moderate AD subject subscale, or
 - ADL in MCI subscale for preclinical and prodromal AD subjects
- Neuro Psychiatric Inventory Questionnaire (NPI-Q)

Supervised performance test of the subjects performed at the clinic:

- Physical Functioning Test
 - Gait standard and dual task
 - Timed up-and-go test.

Evaluation of a Computerized Complex Instrumental Activities of Daily Living Marker (NMI) (AltoidaML)

- Spatial memory and navigation task (Altoida Medical Device)

When questionnaires or rating scales are available from the past 6 months, there is no need to fill out the questionnaire again. After completion procedures at the clinic described above, the study participant will receive training for the use of RMT devices in real life, when at home. Briefly, smartphone applications will be installed on their own smartphone of both the subject and caregiver. Each participant will also receive a wrist device and optional, for a brief period, a wearable camera. Caregivers will receive a wrist device as well, if possible with the logistics. A telephone hotline for technical issue will be made available.

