2. OBJECTIVES & OUTCOMES

1. Objectives

The main objective is to assess the performance of selected RMTs against ADL standard clinical questionnaires in finding differences among individuals of various classes of severity of AD and investigate if RMT measurements are more precise and better reflect disease progression and functional /QoL changes compared to ADL standard measurements.

Secondary objectives:

- to assess associations between RMT measurements and standard clinical scales used to assess specific clinical conditions and functional impairments in AD patients;
- to assess if RMT measurements are more precise and more ecological;
- to investigate the patient acceptability and user-friendliness of selected RMTs;
- to assess the technical performance of RMTs in a real-life setting.
- to assess associations between RMT measurements, standard clinical scales and AD-related biomarker in blood and CSF
- to explore new AD-related biomarkers.

To achieve the non-invasive aspect of these objectives, measurements will be performed in clinic (i.e. under supervision of a clinical team) and in non-clinical, real life settings (i.e. at home, at work, etc.).

Primary Outcome

- Difference between healthy controls, subjects with preclinical AD, subjects with MCI due to AD, and subjects with mild-to-moderate AD dementia using selected RMTs measurements aimed to profile ADL, using diagnostic criteria as defined under 3.1.3" Both primary and secondary outcomes.

¹ Buegler, M, Harms, RL, Balasa, M, et al. Digital biomarker-based individualized prognosis for people at risk of dementia. *Alzheimer's Dement*. 2020; 12:e12073. <https://doi.org/10.1002/dad2.12073>

Evaluation of a Computerized Complex Instrumental Activities of Daily Living Marker (NMI) (AltoidaML)

Secondary Outcomes

- Established clinical measures: difference between healthy volunteers, subjects with preclinical AD, subjects with MCI due to AD, and subjects with mild-to-moderate AD dementia in the following assessments of specific functions when performed in the clinic (in brackets, it is indicated which functional domain and/or main outcome measure is covered by the assessment):
 - Amsterdam-iADL
 - (orientation, planning skills & memory required for task completion household management).
 - ADCS-ADL
 - (orientation, planning skills & memory required for task completion household management).
 - CERAD neuropsychological test battery

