Table 2: list of assessments classified by test setting (clinic or real life) and completers.

| Setting | Completed by | Test/device name | Frequency | Time (minutes) | Functional domain(s) and/or test domain(s) covered |
|---------|--------------|---|-----------|----------------|--|
| Clinic | Patient | Demographics, medical history, medication use | Once | 10 | Life habits & AD risk factors |
| | | Physical examination | Once | 10 | Life habits & AD risk factors |
| | | Godin Leisure-time exercise questionnaire | Once | 5 | Life habits & AD risk factors |
| | | CERAD test battery | Once | 20 | |
| | | • Verbal fluency (animal naming) | Once | 5 | Word finding difficulties |
| | | • 15 item Boston Naming Test | Once | 5 | Planning skills & memory, Word finding difficulties |
| | | • Mini Mental State Examination | Once | 5 | Orientation, Planning skills & memory, Word finding difficulties |
| | | • Word list learning | Once | 5 | Word finding difficulties |
| | | • Word list recall | Once | 5 | Planning skills & memory, Word finding difficulties |
| | | • Word list recognition | Once | 5 | Planning skills & memory, Word finding difficulties |
| | | • Constructional praxis | Once | 5 | Planning skills & memory |
| | | • Delayed constructional praxis | Once | 5 | Planning skills & memory |
| | | Digit Symbol Substitution Test | Once | 5 | Planning skills & memory |
| | | Altoida Medical Device | Once | 20 | Orientation, Planning skills & memory |
| | | Physical functioning tests | Annual | 10 | Gait |
| | | • 1-minute walking test | Once | 5 | |
| | | • 1-minute dual walking test | Once | 5 | |
| | | • Timed up-and-go test | Once | 5 | |
| | | Social Functional Scale | Annual | 5 | Maintaining social roles |
| | | Geriatric Depression Scale | Annual | 5 | Motivation |
| | | Body Mass Index (BMI) | Annual | 5 | Life habits & AD risk factors |
| | | Clinical Dementia Rating | Annual | 20 | Orientation, Household management, Use of technology, Maintaining social roles |
| | | ADCS-ADL | Annual | 20 | Orientation, Planning skills & memory, Household management |
| | | Diabetes or pre-diabetes | Annual | 5 | Life habits & AD risk factors |
| | | Clinical Dementia Rating | Annual | 20 | Orientation, Household management, Use of technology, Maintaining social roles |

Evaluation of a Computerized Complex Instrumental Activities of Daily Living Marker (NMI) (AltoidaML)

| | | | | | |
|--|--|---------|------|---|-------------------------------|

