- *The Amsterdam-IADL (A-IADL) questionnaire short version.* This questionnaire consists of 30 questions that explore the functional capacity during daily living activities as observed in the subjects during the last week. The questionnaire includes several questions regarding the use of media and devices [22]. It is scored by the caregiver/family member, can be operated on tablet or PCs and will take 10 minutes to fill in. (www.alzheimercentrum.nl/professionals/amsterdam-iadl/).

Evaluation of a Computerized Complex Instrumental Activities of Daily Living Marker (NMI) (AltoidaML)

- *Clinical Dementia Rating (CDR)*. The CDR is comprised of a semi structured interview one with the with a caregiver. During the interview, the rater assesses the participant's current status in six domains (memory, orientation, judgment and problem solving, community affairs, home and hobbies, and personal care) and rated accordingly using a 5-point scale (0 = no impairment, 0.5 = questionable impairment, 1 = mild dementia, 2 = moderate dementia, 3 = severe dementia, <http://knightadrc.wustl.edu/cdr/aboutcdr.htm>). The outcome measures of the CDR and CSD-SB are CDR scores (derived from an algorithm developed by the Knight ADRC) [23].
- *Alzheimer's Disease Cooperative Study (ADCS) scale*. ADL in mild and moderate AD subject subscale. A questionnaire describing the performance of activities of daily living in patients with Alzheimer's Disease [24]. ADL in MCI subscale for preclinical and prodromal AD subjects. A questionnaire describing the performance of activities of daily living in patients with mild cognitive impairment [25].
- *Neuro Psychiatric Inventory Questionnaire (NPI-Q)*. A questionnaire to assess 12 neuropsychiatric disturbances, e.g. irritability and depression, in dementia patients [26]. This questionnaire is filled out by a caregiver or informant. All 12 items are scores on severity and frequency.

Performance test at the clinic

- *Navigation and Spatial memory test*:

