6. STATISTICAL ANALYSIS

Data obtained from RMTs will be either continuous (as, for example, accelerometer recording having several samples per second, participant's relative locations recorded via GPS every 5 minutes, ...) or obtained during a single clinical visit only (as, for example, gait assessment). Continuous raw data will be analytically processed and features characterizing behaviour per day will be obtained. For example, actigraphy read-outs will be used to derive sleep characteristics using Cole-Kripke algorithm (duration, quality of sleep, etc.) for every night, relative location data will be used to estimate distance travelled per day, duration of home stay per day, number of places visit per day and so on. Complete strategy for handling multi-sensor data and list of relevant features will be developed through the project duration. At the end, RMT data will be either a day-by-day time series or obtained at a single study time point.

We will analyse each RMT measurement separately, characterizing their variance to assess, whether 1) they are different between following groups: (a) healthy volunteers and (b) subjects with preclinical AD, (c) subjects with MCI due to AD, and (d) subjects with mild-to-moderate AD dementia, and 2) whether they are related to standard clinical questionnaires for ADL. For a continuous day-by-day time series, we will model such a RMT measure using a mixed-effect model for repeated measures (MMRM) based on observed case data. The model will include study group (or a related ADL scale), age, sex, and other related covariates/factors. Strength of between study groups difference (or relation to related ADL scale) is of primary interest. The within-participant covariance between visits will be estimated via an unstructured variance-covariance matrix. In case of convergence problems, alternative variance-covariance structures will be tried in the following order, with the first structure that converges being used in the analysis: heterogeneous Toeplitz, standard Toeplitz, and AR(1) with separate participant random effect. Weekdays and weekends time

Evaluation of a Computerized Complex Instrumental Activities of Daily Living Marker (NMI) (AltoidaML)

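### The ADCS ADL form changes with disease stage, so ADCS-ADL contrasts of preclinical AD or MCI with dementia confound form with stage, and contrasts with controls are undefined

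*Combined protocol and SAP*

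**What the plan says.** Section 4.4.2 (Main study, baseline visit) lists the ADCS scale among the informant-rated instruments and offers two alternatives: "ADL in mild and moderate AD subject subscale, or" then "ADL in MCI subscale for preclinical and prodromal AD subjects".

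Assessments in the clinic repeats this split and treats each alternative as a questionnaire with its own reference (24 for the dementia form, 25 for the MCI form). The second is described as "A questionnaire describing the performance of activities of daily living in patients with mild cognitive impairment". Neither place says which form healthy controls receive, although controls are an enrolled group (215 in the inclusion criteria).

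The Secondary Outcomes introduce a list that contains ADCS-ADL, undivided, with the words "Established clinical measures: difference between healthy volunteers, subjects with preclinical AD, subjects with MCI due to AD, and subjects with mild-to-moderate AD dementia in the" assessments named below. Table 2 also has a single row: "ADCS-ADL | Annual | 20 | Orientation, Planning skills & memory, Household management".

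The Statistical Analysis section says of the repeated-measures model for each RMT: "The model will include study group (or a related ADL scale), age, sex, and other related covariates/factors". The ANCOVA for single-visit RMTs has the same alternative, and the later prediction models may target either study group or a related ADL scale. The section does not mention the two ADCS forms and gives no rule for linking, rescaling or separating them.

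**The concern.** A group difference on a rating scale can be read as a difference in function only if the groups were measured with the same scale. Here the questionnaire is decided by diagnostic group, and it changes at the boundary between MCI and dementia. An observed ADCS-ADL step at that boundary could reflect functional loss, different items and scoring, or both. A step could also be masked.

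The same problem enters any RMT model that takes ADCS-ADL as the ADL term and pools participants from both sides of the boundary. Part of the fitted relation between RMT and ADL would then come from the switch of form. The main objective is to judge RMTs against standard ADL questionnaires, so the choice of reference scale matters there too.

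**Working it through.** The documents give no ADCS-ADL effect size, SD or power, so there is no figure of the plan's to reproduce. The check is structural.

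**Step 1: what a contrast estimates.** Write the mean observed score in group g as T(g) + F(form given to g), where T is function and F is the contribution of the form. Then:

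- MCI minus dementia = [T(MCI) − T(dementia)] + [F(MCI form) − F(dementia form)].
- Preclinical minus MCI = T(preclinical) − T(MCI), because the form terms cancel.

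The first line has two unknown brackets and one observed difference. No group is stated to receive both forms, so the form bracket cannot be estimated. Adjusting for age, sex or other covariates does not help, because form is fixed by group.

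**Step 2: the six pairwise contrasts.**

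| Contrast | As written | If controls get the MCI form | If controls get the dementia form |
|---|---|---|---|
| Control vs preclinical | undefined | same form | confounded |
| Control vs MCI | undefined | same form | confounded |
| Control vs dementia | undefined | confounded | same form |
| Preclinical vs MCI | same form | same form | same form |
| Preclinical vs dementia | confounded | confounded | confounded |
| MCI vs dementia | confounded | confounded | confounded |

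As written, one contrast is clean, two are confounded and three are undefined. Naming the control form leaves three of six confounded (MCI form) or four of six (dementia form). Neither choice rescues preclinical or MCI versus dementia.

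**Step 3: the RMT models.** If ADCS-ADL replaces study group, the model contains no term that carries the form. A form-driven step between MCI and dementia is then absorbed into the slope of RMT on ADCS-ADL. Models fitted within groups that share a form do not have this problem.

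**Step 4: how large an offset would matter.** This illustrates consequences; it does not estimate the bias. Assumptions: 55 per group (the plan's per-group minimum, derived for the Amsterdam iADL), within-group SD of 1, a two-sided 5% test without multiplicity adjustment, and a form offset of 0.1 to 0.8 SD chosen only to show a range. With no true MCI–dementia difference, the chance of p<0.05 is about Φ(offset × √(55/2) − 1.96), where √27.5 = 5.244. The opposite tail adds less than one percentage point.

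| Assumed offset (SD) | Offset × 5.244 − 1.96 | Chance of p<0.05 |
|---|---|---|
| 0.1 | −1.436 | about 8% |
| 0.2 | −0.911 | about 18% |
| 0.3 | −0.387 | about 35% |
| 0.5 | 0.662 | about 75% |
| 0.8 | 2.235 | about 99% |

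With an assumed true difference of 0.6 SD, power is about 88% (0.6 × 5.244 − 1.96 = 1.186). An opposing offset of 0.3 SD leaves a net 0.3 SD and about 35%. A reinforcing one gives a net 0.9 SD and more than 99%. A modest offset in either direction could therefore change the conclusion. The documents do not show whether one exists.

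**The case against.** Several points can fairly be made for the plan.

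- **A common yardstick exists.** The Amsterdam IADL is listed at baseline without any split by stage, and the Secondary Outcomes give it the same functional domains as ADCS-ADL. This stands: cross-stage comparison of ADL does not depend on ADCS-ADL.
- **ADCS-ADL has a small analytic role.** It is one entry in a long secondary list, no model for its group comparison is specified, and the sample size rests on the Amsterdam iADL. This stands and limits the severity.
- **The missing control form may be a wording gap.** The title of reference 25 concerns telling MCI patients from healthy elderly people, which hints at the MCI form. That is plausible but not stated, and the contrasts with dementia would remain confounded.
- **The two forms may be on a common footing.** Section 4.4.2 calls them subscales of one scale. But Assessments in the clinic describes separate questionnaires with separate references, and nothing says that their scores are interchangeable.

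A reader might go further and infer that the primary objective is compromised, particularly because the sample size section counts the web-based Amsterdam iADL among the RMTs, which would leave ADCS-ADL as the only ADL reference. The documents do not support that. The Secondary Outcomes list the Amsterdam iADL among the established clinical measures, and the Statistical Analysis section names no ADL scale.

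**Conclusion.** The point holds for ADCS-ADL contrasts of preclinical AD or MCI with dementia, and for any pooled RMT model that uses ADCS-ADL across that boundary. In these, form and stage cannot be separated by any analysis the plan describes. Preclinical AD versus MCI is sound. Contrasts with controls are unspecified, not shown to be biased.

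The size and direction of the bias cannot be estimated from the documents. A reader might infer a distortion of one or more SD from differing score ranges, but no ranges, item lists or SDs are given, and the plan does not say that raw totals will be compared. A reader might also infer that within-person change over the annual assessments is distorted. The plan does not say that a participant's form changes when the stage does, so that is an open question.

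The effect is on a secondary outcome. It reaches the primary objective only where ADCS-ADL is chosen as the ADL reference. The sample size and the Amsterdam IADL comparison are unaffected. The conclusion assumes that the forms are given as section 4.4.2 states, with no group receiving both. It should be corrected, but it does not threaten the study as a whole.

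**What to change.** 1. State in section 4.4.2 and in Assessments in the clinic which ADCS form controls receive.
2. In the Secondary Outcomes and Statistical Analysis sections, limit ADCS-ADL group contrasts and RMT–ADCS-ADL models to groups that share a form, with the other form's participants analysed separately. Alternatively, define a score from items confirmed, from both item lists, to be common to the two forms.
3. Name the Amsterdam IADL as the scale for ADL comparisons and pooled RMT models that span the dementia boundary.
4. Record the form used at each assessment, since section 4.4.2 allows questionnaires from the past 6 months to be reused, and say whether the form follows baseline group or current stage at the annual repeats.

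The restriction costs only protocol and SAP wording, but the ADCS-ADL contrast of preclinical AD or MCI with dementia is lost. A common-item score keeps that contrast but needs scoring work and gives up some item coverage; how much cannot be judged from the documents. Giving everyone one form would also remove the confounding. It changes what is administered, however, and the documents do not show that either form suits the whole range from controls to moderate dementia, so it is an option to weigh and not the default.
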